8.1 Primary Objective

1. To estimate the incidence rate of stroke (ischemic or hemorrhagic), major bleeding and death in both non-valvular AF patients exposed to OAC (VKA or DOAC) and unexposed to OAC, overall and in the following subgroups of interest:
 - Elderly (≥ 80 years old)
 - Patients with CAD
 - Frail patients
 - Patients reported with active cancer
 - Patients reported with previous stroke

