Name of the analysis	To estimate the incidence rate of stroke (ischemic or hemorrhagic), major bleeding and death in both AF patients (exposed and unexposed to OAC)	To describe the characteristics of AF patients exposed and unexposed to OAC	To compare the incidence rate of stroke, major bleeding, and death between those two populations	To estimate the annual incidence and prevalence of patients with AF, exposed and unexposed to OAC	To describe the use of oral anticoagulants (OACs) in AF patients initiating treatment (AF patients exposed to OAC therapy)	To compare the Healthcare Resource Utilization (HCRU) and associated costs between patients exposed to apixaban, rivaroxaban, dabigatran, VKA and patients unexposed to OACs	To describe the therapeutic management before/after the first stroke occurring after initiation of OAC exposure	To identify subgroups among AF patients with similar profile
Outcomes	Estimation of the incidence rate of stroke, major bleeding, and death. Incidence rate in unexposed patients will be standardized on age using the exposed to OAC group as population of reference.	Description of sociodemographic characteristics, comorbidities, medical history of interest and concomitant treatments	Comparison of incidence rate in longitudinal analysis for each event of interest (stroke, major bleeding, and death)	Estimation of the annual incidence and prevalence of patients with AF. Annual incidence will be standardized on age using INSEE data (French population) as population of reference	Description of the use of oral anticoagulants (OACs) in AF patients initiating treatment (AF patients exposed to OAC therapy)	Comparison of the Healthcare Resource Utilization (HCRU) and associated costs between patients exposed to apixaban, rivaroxaban, dabigatran, VKA and patients unexposed to OACs	Description of the therapeutic management before/after the first stroke occurring after initiation of OAC exposure	Identification of subgroup of AF patients with similar profile

Periods	2016 - 2019	2016-2019 (per calendar year)	2016 - 2019	2014 – 2019 (per calendar year)	2016 - 2019	2016 - 2019	2016 - 2019	2016 - 2019
Populations	Incident AF patients	Incident AF patients	Incident AF patient	All AF patients (prevalent & incident)	Incident AF patients exposed to OAC	Incident AF patients exposed and unexposed to OAC	Incident AF patients exposed to OAC	Incident AF patients exposed and unexposed to OAC

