9.7.3 Planned Analysis for the Primary Objective

9.7.3.1 To estimate the incidence rate of stroke (ischemic or hemorrhagic), major bleeding and death in AF patients exposed to OAC (VKA or DOAC) and unexposed to OAC

The analysis of incidence rate for the first occurrence of each event of interest (stroke, major bleeding and death) will be conducted in the population of AF incident patients excluding those with a reported outcomes of interest up to 30 days prior index date.

As a reminder, incident AF patients will be the patients newly diagnosed AF during the inclusion period i.e., with a date of first diagnosis of AF, identified by the date of the start of LTD or of the index hospital stay during inclusion period, or the date of initiation of the OAC.

Event rates will be estimated over the 4-year period 2016-2019, in the overall population and according to the treatment exposure.

The incidence rate for each event of interest (stroke, major bleeding and death) will be defined as the number of events occurring during the follow-up period divided by the number of person-years of follow-up (sum of durations of follow-up period for incident patients).

Incidence rates in unexposed patients will be standardized by age using exposed patients as the population of reference.

Analyses will be descriptive in nature (proportion and 95% confidence interval).

Event rates will also be displayed by sub-populations (see section [9.2.3.4](#)).

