Death	xx.x (xx.x)	xx.x (xx.x)	xx.x (xx.x)
Lost to follow-up	xx.x (xx.x)	xx.x (xx.x)	xx.x (xx.x)
End of study period	xx.x (xx.x)	xx.x (xx.x)	xx.x (xx.x)
Duration of the follow-up in years			
Mean (std)	xx.x (xx.x)	xx.x (xx.x)	xx.x (xx.x)
Median	xx.x	xx.x	xx.x
Q1 - Q3	xx.x - xx.x	xx.x - xx.x	xx.x - xx.x
Min - Max	xx.x - xx.x	xx.x - xx.x	xx.x - xx.x
Duration group of the follow-up in years: n (%)			
[0-1[xx.x (xx.x)	xx.x (xx.x)	xx.x (xx.x)
[1-2[xx.x (xx.x)	xx.x (xx.x)	xx.x (xx.x)
[2-3[xx.x (xx.x)	xx.x (xx.x)	xx.x (xx.x)
[3-4[xx.x (xx.x)	xx.x (xx.x)	xx.x (xx.x)
[4-5]*	xx.x (xx.x)	xx.x (xx.x)	xx.x (xx.x)

*This category will be display only for the sensitivity analysis (up to 2020)

2. Shell Tables and Figures of Results of the Planned Analysis for the Primary Objective

Table A2. Incidence rate for stroke, major bleeding and death in AF incidents patients between 2016 and 2019 in France – <POPULATION>

<POPULATION>	Stroke				Major bleeding				Death			
	n	N	Crude	Standardized **	n	N	Crude	Standardized %**	n	N	Crude	Standardized **
Overall	x	x	x,x [x,x;x,x]	NA	x	x	x,x [x,x;x,x]	NA	x	x	x,x [x,x;x,x]	NA
CI 95%				NA				NA				NA
Unexposed to OAC*	x	x	x,x [x,x;x,x]	x,x [x,x;x,x]	x	x	x,x [x,x;x,x]	x,x [x,x;x,x]	x	x	x,x [x,x;x,x]	x,x [x,x;x,x]
CI 95%												
Exposed to OAC	x	x	x,x [x,x;x,x]	NA	x	x	x,x [x,x;x,x]	NA	x	x	x,x [x,x;x,x]	NA
CI 95%				NA				NA				NA
VKAs	x	x	x,x [x,x;x,x]	NA	x	x	x,x [x,x;x,x]	NA	x	x	x,x [x,x;x,x]	NA
CI 95%				NA				NA				NA
DOACs	x	x	x,x [x,x;x,x]	NA	x	x	x,x [x,x;x,x]	NA	x	x	x,x [x,x;x,x]	NA
CI 95%				NA				NA				NA
Apixaban	x	x	x,x [x,x;x,x]	NA	x	x	x,x [x,x;x,x]	NA	x	x	x,x [x,x;x,x]	NA
CI 95%				NA				NA				NA
Dabigatran	x	x	x,x [x,x;x,x]	NA	x	x	x,x [x,x;x,x]	NA	x	x	x,x [x,x;x,x]	NA
CI 95%				NA				NA				NA
Rivaroxaban	x	x	x,x [x,x;x,x]	NA	x	x	x,x [x,x;x,x]	NA	x	x	x,x [x,x;x,x]	NA
CI 95%				NA				NA				NA

OAC: Oral anticoagulant; DOACs: Direct oral anticoagulants; VKAs: Antivitamins K; NA, not applicable.

n: number of events of interest; N: number of person-years of follow-up

*Unexposed and exposed to OAC correspond to the period of time where the patients are not exposed to OAC and exposed to OAC, respectively

%: Incidence of the event of interest; CI 95%: 95% confidence interval

**: Standardized on age group (<65 years old; 65-74 years old; 75-79 years old; ≥80 years old) using the exposed population as reference

<POPULATION>: Incidence rate of events will be stratified in the following sub-groups:

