Incident elderly AF patient (≥80 years old)

Incident AF patient having a history of coronary arterial disease (CAD)

Incident AF frail patient

Incident AF patient having an active cancer

Incident AF patient reported with previous stroke

Modified CHAD2DS2VASC score groups (Low risk / Moderate risk/ High

This table will be presented for sensitivity analyses:

- with integration of 2020 data;
- with a grace period of 30 days and 90 days;
- with integration of all incident AF patients (i.e. inclusion of patients with an event of interest between inclusion date and index date).

Table A3. Incidence rate for ischemic and hemorrhagic stroke in AF incidents patients between 2016 and 2019 in France

<POPULATION>	Stroke							
	Ischemic				Hemorrhagic			
	n	N	Crude	Standardized **	n	N	Crude	Standardized **
Overall	x	x	x,x	NA	x	x	x,x	NA
CI 95%			[x,x;x,x]	NA			[x,x;x,x]	NA
Unexposed to OAC*	x	x	x,x	x,x	x	x	x,x	x,x
CI 95%			[x,x;x,x]	[x,x;x,x]			[x,x;x,x]	[x,x;x,x]
Exposed to OAC*	x	x	x,x	x,x	x	x	x,x	x,x
CI 95%			[x,x;x,x]	[x,x;x,x]			[x,x;x,x]	[x,x;x,x]
VKAs	x	x	x,x	x,x	x	x	x,x	x,x
CI 95%			[x,x;x,x]	[x,x;x,x]			[x,x;x,x]	[x,x;x,x]
DOACs	x	x	x,x	x,x	x	x	x,x	x,x
CI 95%			[x,x;x,x]	[x,x;x,x]			[x,x;x,x]	[x,x;x,x]
Apixaban	x	x	x,x	x,x	x	x	x,x	x,x
CI 95%			[x,x;x,x]	[x,x;x,x]			[x,x;x,x]	[x,x;x,x]
Dabigatran	x	x	x,x	x,x	x	x	x,x	x,x
CI 95%			[x,x;x,x]	[x,x;x,x]			[x,x;x,x]	[x,x;x,x]
Rivaroxaban	x	x	x,x	x,x	x	x	x,x	x,x
CI 95%			[x,x;x,x]	[x,x;x,x]			[x,x;x,x]	[x,x;x,x]

OAC: Oral anticoagulant; DOACs: Direct oral anticoagulants; VKAs: Antivitamins K; NA, not applicable.

n: number of events of interest; N: number of person-years of follow-up

*Unexposed to OAC and exposed to OAC correspond to the period of time where the patients are not exposed to OAC and exposed to OAC respectively

** Standardized on age group (<65 years old; 65-74 years old; 75-79 years old; ≥80 years old) using the exposed population as reference.

3. Shell Tables and Figures of Results of the Planned Analysis for the Secondary Objectives

3.1. To describe the characteristics of AF incidents patients at index date, per year

Table A4. Description of sociodemographic characteristics in AF incident patients at index date, per year

	Exposed to OAC				Total exposed to OAC			Unexposed to OAC			Total unexposed To OAC	
	2016 (N=XXX)	2017 (N=XXX)	2018 (N=XXX)	2019 (N=XXX)	2016-2019 (N=XXX)	2016 (N=XXX)	2017 (N=XXX)	2018 (N=XXX)	2019 (N=XXX)	2016-2019 (N=XXX)		

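### Table A2 age-standardises only the unexposed rate, so the crude VKA, DOAC and single-agent rows beside it are not age-comparable with it or with each other, and Table A3 follows a different rule

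*SAP*

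**What the plan says.** The primary objective (SAP 8.1) is to estimate rates of stroke, major bleeding and death "in both non-valvular AF patients exposed to OAC (VKA or DOAC) and unexposed to OAC". Four places say how age is handled.

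- **SAP 9.7.3:** "Incidence rates in unexposed patients will be standardized by age using exposed patients as the population of reference". The same section calls the analysis descriptive.
- **SAP 9.7.1, Table XXI, primary column:** "Incidence rate in unexposed patients will be standardized on age using the exposed to OAC group as population of reference".
- **Table A2 (all three events):** the unexposed row has a standardised rate with a confidence interval. The VKA row reads "VKAs x x x,x [x,x;x,x] NA", and the DOAC and single-agent rows follow the same pattern. The abbreviations line defines NA: "OAC: Oral anticoagulant; DOACs: Direct oral anticoagulants; VKAs: Antivitamins K; NA, not applicable". The footnote gives the method: "Standardized on age group (<65 years old; 65-74 years old; 75-79 years old; ≥80 years old) using the exposed population as reference".
- **Table A3 (ischemic and hemorrhagic stroke):** its footnote has the same bands and reference, but the VKA row reads "VKAs x x x,x x,x x x x,x x,x", so the standardised column is filled. The pooled exposed, DOAC and single-agent rows are filled too.

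Nothing in the text explains why the two tables differ.

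**The concern.** Table A2 lists unexposed time, pooled exposed time, VKAs, DOACs and each agent one under the other. By standardising the unexposed rate, the plan accepts that crude rates mislead when age mixes differ. That reasoning applies equally to a subset of the exposed: VKA users, or users of one DOAC, need not have the age mix of all exposed person-time. A reader who sets the standardised unexposed rate against the crude VKA or apixaban rate is comparing figures on different age footings.

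The A2/A3 conflict adds a practical problem. The programmer must either go beyond 9.7.3 to fill A3 or leave A3 cells empty. As the shells stand, hemorrhagic stroke by agent would have a standardised rate. Major bleeding by agent, which includes the same intracranial codes (Table VIII), would not.

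At stake is the reading of the primary absolute rates by agent. Protocol 2.4 foresees using the results to support submissions to health authorities.

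**Working it through.** **Step 1. Shells side by side (standardised column).**

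| Row | A2 | A3 |
|---|---|---|
| Overall | NA | NA |
| Unexposed | filled | filled |
| Pooled exposed | NA | filled |
| VKAs, DOACs, each agent | NA | filled |

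**Step 2. Where NA is right.** The directly standardised rate is Σ wᵢrᵢ over the four bands, with wᵢ the share of all exposed person-years in band i. For the pooled exposed row these weights are its own, so the result is the crude rate. NA is correct there, and the filled A3 cell would only repeat the crude figure. For VKAs, DOACs or one agent the weights are not the row's own, so standardisation is applicable and can change the rate.

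**Step 3. Size.** The plan states no figure to reproduce, and it gives neither age-specific rates nor an age mix by agent. The inputs below are assumptions. Age-specific rates are identical for VKA and DOAC, so the true ratio is 1.00. VKA is arbitrarily taken as the older group, with 30% of exposed person-years. Mixes are shares of person-time at <65, 65-74, 75-79 and ≥80; rates are per 100 person-years.

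*Low case.* Rates 1, 1.3, 1.6, 2.0 (≥80 is 2x <65); share aged ≥80 is 45% vs 40%.
- VKA: 0.15×1 + 0.25×1.3 + 0.15×1.6 + 0.45×2.0 = 1.615
- DOAC: 0.18×1 + 0.27×1.3 + 0.15×1.6 + 0.40×2.0 = 1.571
- Ratio: 1.03

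*Middle case.* Rates 0.8, 1.4, 2.2, 3.2 (4x); share aged ≥80 is 50% vs 35%.
- VKA: 0.13×0.8 + 0.22×1.4 + 0.15×2.2 + 0.50×3.2 = 2.342
- DOAC: 0.20×0.8 + 0.30×1.4 + 0.15×2.2 + 0.35×3.2 = 2.030
- Ratio: 1.15

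*High case.* Rates 1.5, 3, 6, 15 (10x); share aged ≥80 is 60% vs 30%.
- VKA: 0.08×1.5 + 0.17×3 + 0.15×6 + 0.60×15 = 10.53
- DOAC: 0.25×1.5 + 0.30×3 + 0.15×6 + 0.30×15 = 6.675
- Ratio: 1.58

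**Step 4. After standardising both rows.** In the middle case the pooled weights give 0.3×2.342 + 0.7×2.030 = 2.124 for each drug, a ratio of 1.00. The ratio is 1.00 in every case, because the age-specific rates are identical by assumption.

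**Step 5. Age in the Cox model.** SAP 9.7.4.2 codes age as <80, 80-90 and >90, so differences below 80 are left to other covariates. In the middle case the crude rates under 80 are 0.742/0.50 = 1.484 and 0.910/0.65 = 1.400, a ratio of 1.06. Across the assumed cases this residual ratio runs from 1.01 to 1.23. It is before the other covariates; Table XV includes CHA2DS2-VASc and the age-adjusted Charlson index, which both contain age.

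**The case against.** The strongest reply is that Table A2 is not meant to compare agents. The primary objective estimates rates in exposed and unexposed patients, and for that contrast standardising the unexposed to the exposed age mix is coherent. Comparison is a separate objective, met by a time-dependent Cox model with VKA as reference and adjustment for age and many other factors (9.7.4.2, Table A10). The agent cells in A2 are labelled crude, and Table A7 describes age by agent. All of this stands.

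A reader might go further and infer that the plan presents age differences as drug effects, or that it has no age-adjusted comparison of agents. The documents support neither. A2 claims no adjustment for those rows, and Table A10 supplies adjusted hazard ratios.

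A reader might also take A3 as the intended rule and A2 as the error. Three places agree on standardising the unexposed only, and A3 even fills the redundant pooled cell, so A3 may be the slip. Setting those A3 cells to NA would be the smallest edit. It would remove the conflict but leave the agent rows in A2 without an age-comparable rate. Hazard ratios against VKA do not supply absolute rates on a common age footing, and the planned standardised column can.

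Finally, age-only standardisation leaves prior stroke, bleeding history, frailty and co-medication unadjusted, and could itself invite head-to-head reading. That is a fair reason for a footnote.

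**Conclusion.** The point holds as a limit on how the primary table can be read and as an inconsistency between two shells. In Table A2 the standardised unexposed rate is age-comparable with the pooled exposed row only. The VKA, DOAC and agent rows are crude, and are age-comparable neither with it nor with each other. No planned rate is computed wrongly, and the formal agent comparison lies in the Cox model, although its age bands are coarse.

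Age alone could give a crude VKA/DOAC ratio of about 1.03 to 1.58, with 1.15 in the middle case, when the true ratio is 1.00. This rests wholly on the assumed age mixes and rate gradients. The documents do not show which agents have older users, so the direction is unknown and no single figure should be quoted as the expected distortion. The ≥80 version of A2 is unaffected, because it is one age band. The change is worth making before analysis because it is cheap.

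**What to change.** 1. In SAP 9.7.3, Table XXI and Table A2, keep the crude column. Also directly standardise the VKA, all-DOAC, apixaban, dabigatran and rivaroxaban rates, alongside the unexposed rate, to the four-band age distribution of all exposed person-time. Say person-time explicitly: the table's denominators are person-years, whereas 9.7.3 speaks of patients.
2. Apply the same rule in Table A3. Show NA for the pooled exposed row in both tables, because it is the reference.
3. Footnote both tables: rates are standardised for age only, and adjusted agent comparisons are in Table A10.

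The cost is the planned code run on five more rows of A2 and its repeats, a sentence in 9.7.3, and matching edits to Table XXI and the shells. The downside is more output, and age-only rates that might be read as head-to-head comparisons, which the footnote addresses.

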3.7.1 Outcomes of primary objectives

Estimation of incidence rate of stroke, major bleeding, and death in both non-valvular AF patients exposed to OAC (VKA or DOAC) and unexposed to OAC, overall and in the subgroups of interest.

In longitudinal analyses, for each AF populations and subpopulations of interest defined in section 3.2.2, the annual cumulative incidence will be estimated from the occurrence of each of the events of interest, stroke, major bleeding, and death, during patient follow-up. The annual cumulative incidence will be defined as the number of events occurring during the follow-up period divided by the number of person-years of follow-up.

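### The primary event rates have a person-year denominator, but the SAP names a proportion interval for them and gives no formula; a rate-based interval should be specified.

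*SAP*

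**What the plan says.** SAP 9.7.3.1 sets the numerator as first events: "The analysis of incidence rate for the first occurrence of each event of interest (stroke, major bleeding and death"). The event count is then "divided by the number of person-years of follow-up (sum of durations of follow-up period for incident patients"). The period is also stated: "Event rates will be estimated over the 4-year period 2016-2019, in the overall population and according to the treatment exposure".

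The only sentence on how uncertainty is reported reads "Analyses will be descriptive in nature (proportion and 95% confidence interval").

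Shell Table A2 (SAP Appendix 3) defines its two counts as "n: number of events of interest; N: number of person-years of follow-up". The table has no column for patients. Its footnote attaches a percent sign to this definition: "Incidence of the event of interest; CI 95%: 95% confidence interval". One of the column heads, the standardised column under major bleeding, also carries a percent sign. Table A3 uses the same two counts and has no percent sign.

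Protocol 3.7.1 gives the same ratio a proportion-type name: "The annual cumulative incidence will be defined as the number of events occurring during the follow-up period divided by the number of person-years of follow-up". The SAP abstract and SAP 9.7.3.1 call it an incidence rate.

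Neither document states a distribution, formula or procedure for the interval around the crude or the age-standardised rates.

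**The concern.** A proportion interval assumes N independent units, each of which either has the event or does not. Person-years are not such units: a patient may contribute a few days or up to four years. The sampling variance of a rate comes from the event count, about n/N², whereas a proportion interval uses p(1 − p)/N. The second is always smaller, and the gap grows with the rate.

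The sentence governs the interval for the primary objective. SAP 9.6 tells the statistician to follow the instructions in the signed-off plan, so the wording could reach the program unchanged. The outcome most exposed is death in the subgroups with the highest mortality. In a side-by-side reading, the row with the higher rate would look more precise than it is.

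**Working it through.** **Figure in the plan to reproduce.** None. The documents state no expected rate, event count, interval width or precision target for these rates. The rates below are assumptions, and the range runs from 2 to 30 per 100 person-years (PY).

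**Inputs from the documents.** Estimate r = n/N, with n first events and N person-years (SAP 9.7.3.1, Table A2). The level is 95%, so z = 1.960. Follow-up varies within the four years 2016–2019.

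**Formulas.**
- Proportion interval with person-years as N: r ± z·sqrt(r(1 − r)/N)
- Rate (Poisson) interval: r ± z·sqrt(r/N)
- Ratio of widths: sqrt(1 − r), whatever N is
- Approximate true coverage of the proportion interval: 2Φ(z·sqrt(1 − r)) − 1

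**Results for N = 1,000 PY** (rates and limits per 100 PY):

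| Assumed rate | Proportion interval | Rate interval | Width ratio | Narrower by | Coverage by formula |
|---|---|---|---|---|---|
| 2 | 1.13–2.87 | 1.12–2.88 | 0.990 | 1.0% | 94.8% |
| 10 | 8.14–11.86 | 8.04–11.96 | 0.949 | 5.1% | 93.7% |
| 20 | 17.52–22.48 | 17.23–22.77 | 0.894 | 10.6% | 92.0% |
| 30 | 27.16–32.84 | 26.61–33.39 | 0.837 | 16.3% | 89.9% |

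Exact limits (Clopper–Pearson against exact Poisson) give almost the same width ratios: 0.989, 0.948, 0.895 and 0.838.

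**Simulation.** 10,000 cohorts of 1,000 patients, constant hazard, censoring uniform over 0–4 years. Coverage of the proportion interval against the rate interval was 94.1% v 94.5% at 2 per 100 PY, 93.4% v 94.6% at 10, 92.1% v 94.8% at 20, and 90.1% v 94.8% at 30. With gamma frailty of variance 1 and base hazards of 10 and 30 per 100 PY, coverage was 93.4% v 94.7% and 90.3% v 94.0%.

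**Dependence on the time unit.** Take 300 deaths in 1,000 PY.
- In years: p = 300/1,000 = 0.30. Half-width 1.960·sqrt(0.30·0.70/1,000) × 100 = 2.84 per 100 PY.
- In months: p = 300/12,000 = 0.025. Half-width 1.960·sqrt(0.025·0.975/12,000) × 1,200 = 3.35 per 100 PY.
- Rate interval: 1.960·sqrt(300)/1,000 × 100 = 3.39 per 100 PY in either unit.

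An interval for the same data should not change with the unit of time.

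**Absolute size in large rows.** At an assumed 30 per 100 PY, the half-widths (proportion v rate) are 0.90 v 1.07 per 100 PY with 10,000 PY, and 0.28 v 0.34 with 100,000 PY.

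**The case against.** The strongest reply is that the word for proportion may be no more than loose drafting. The heading of SAP 9.7.3.1, the rest of its text and the titles of Tables A2 and A3 all speak of rates, and the SAP drops the protocol's cumulative-incidence label. No formula is written. A reader might infer that the plan does treat each person-year as an independent yes/no trial, so that the reported intervals will be too narrow. The documents do not support that as a statement of fact; it is an inference from one word. A proportion of patients is a third possible reading, and would be a different inconsistency.

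This limits the point but does not remove it. If a rate was meant, the primary interval is unspecified. If a proportion of patients was meant, it contradicts the person-year definition. The same correction is needed in each case.

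The reply on size also stands in large part. At the planned scale most intervals will be narrow either way, no test or decision uses them, and the exposed/unexposed comparison has its own hazard-ratio intervals from the Cox model. Small rows are still possible, because SAP 9.7.1 allows reporting down to 10 patients.

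The percent label is a lesser matter: one footnote and one column head in Table A2, and none in Table A3.

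A reader might also argue that splitting a patient's time over several exposure sequences makes matters worse. That adds nothing here. Only first events are counted, and dividing person-time does not in itself invalidate a rate variance.

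**Conclusion.** The interval named for the primary rates does not fit the quantity defined, and no formula resolves the mismatch. If programmed literally on person-years, the interval would be too narrow by sqrt(1 − rate) and would depend on the time unit. The narrowing is about 5% or less up to 10 per 100 PY, and passes 10% only near 20.

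It is tempting to conclude that the death intervals for frail, active-cancer or unexposed patients will be materially wrong. The documents give no mortality figure for any row, so that cannot be shown. The SAP's active-cancer definition is also broad: any listed code in the two years before index, including the in situ and uncertain-behaviour groups. The coverage figures rest on assumed rates, constant or gamma-mixed hazards and uniform censoring.

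Point estimates and the Cox analysis are unaffected. The correction is worth making because it concerns the primary objective and costs almost nothing.

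**What to change.** - In SAP 9.7.3.1, replace the parenthesis in the sentence on descriptive analysis with: incidence rate per 100 person-years with a 95% rate-based confidence interval (for example Poisson). Apply it to all crude rates in Tables A2 and A3.
- For the age-standardised unexposed rates, state the matching variance: the sum over age groups of wᵢ²·nᵢ/Nᵢ², where the weights wᵢ come from the exposed reference population, nᵢ is the number of events and Nᵢ the person-years.
- Remove the percent sign from the Table A2 footnote and from the one standardised column head that carries it. State the unit as per 100 person-years in Tables A2 and A3.

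The cost is SAP wording and table labels, with no new data. If a proportion interval would otherwise have been programmed, the death-rate intervals become wider: by 1/sqrt(1 − r) − 1, which is about 5% at 10 per 100 PY and about 20% at 30 (1/0.837 = 1.195).
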